10.1.9 DATA HANDLING AND RECORD KEEPING

10.1.9.1 DATA COLLECTION AND MANAGEMENT RESPONSIBILITIES

The data issues to be described in this section are covered in Section 10.1.8.

10.1.9.2 STUDY RECORDS RETENTION

Study data will be maintained for at least 10 years after final data collection.

10.1.10 PROTOCOL DEVIATIONS

This study will follow the protocol deviation guidelines from the UNC IRB, as outlined below:

Purpose: To record all protocol deviations that occur at a study site for both observational and interventional clinical research studies.

IMPORTANT: This log is maintained in the Study Binder (Synonyms for this binder include Investigator Binder, Regulatory Binder, Investigator Site File [ISF], and Study File.) and should be made available upon request for review by the IRB and the Sponsor's monitor. Deviations should be reported to the IRB of record as per the IRB Standard Operating Procedures. See OHRE/IRB SOP 1401 for reporting requirements for deviations to the UNC IRB.

Audience/User: Study coordinators, principal investigators (PIs), other site staff, clinical monitor

Best Practice Recommendations:

- Record protocol deviations in the tracking log as they occur, to ensure completeness and accuracy of the data.
- The site PI should sign each form after it has been completed or immediately prior to a monitoring visit. If it has been signed with fewer than five deviations entered into it, the next identified deviation should be reported on a new page to ensure that all deviations have been reviewed by the PI.
- Number each page and identify the final page of the log by indicating FINAL in the page number field.
- Store pages in reverse chronological order, with the newest pages of the log placed at the front of the section.
- Remove this page before using the log.

***DEVIATION CATEGORIES:**

- A. Informed Consent
- B. Eligibility
- C. Protocol implementation
- D. Reporting
- E. Other, specify in log

****DEVIATION CODES:** Numbers listed by the sample protocol deviations

Informed Consent (Category A)

1. Failure to obtain informed consent
2. Consent form used was not current IRB-approved version
3. Consent form does not include updates or information required by IRB
4. Consent form missing

5. Consent form not signed and dated by participant
6. Consent form does not contain all required signatures
7. Other, specify in log

Eligibility (Category B)

8. Participant did not meet eligibility criterion
9. Randomization of an ineligible participant
10. Participant randomized prior to completing Baseline Assessment, etc.
11. Randomization and/or treatment of participant prior to IRB approval of protocol
12. Other, specify in log

Protocol implementation (Category C)

13. Failure to keep IRB approval up to date
14. Participant receives wrong treatment
15. Participant seen outside visit window
16. Use of unallowable concomitant treatments
17. Prescribed dosing outside protocol guidelines
18. Missed assessment
19. Laboratory tests not done
20. Missed visit
21. Other, specify in log

Reporting (Category D)

22. Not submitting reportable information to the IRB within 7 days
23. Failure to respond to the NSI stipulations in the requested timeframe
24. Other, specify in log

Other (Category E)

25. Other, specify in log

IRB Study #		Site Name/Number:	
Protocol Title (Abbreviated):		Protocol ID/Number:	

Principal Investigator:					Page number [1]:				
Ref No.	Subject ID	Date of Deviation	Date Identified	Deviation Description	Dev. Type [2]	Resulted in AE?	Did Subject Continue in Study?	Meets IRB Reporting Req. (i.e. NSI) (Yes/No)	IRB Reporting Date
1									
2									
3									
4									
5									
6									
7									

10.1.11 PUBLICATION AND DATA SHARING POLICY

This study will be conducted in accordance with the following publication and data sharing policies and regulations:

National Institutes of Health (NIH) Public Access Policy, which ensures that the public has access to the published results of NIH funded research. It requires scientists to submit final peer-reviewed journal manuscripts that arise from NIH funds to the digital archive PubMed Central upon acceptance for publication.

This study will comply with the NIH Data Sharing Policy and Policy on the Dissemination of NIH-Funded Clinical Trial Information and the Clinical Trials Registration and Results Information Submission rule. As such, this trial will be registered at ClinicalTrials.gov, and results information from this trial will be submitted to ClinicalTrials.gov. In addition, every attempt will be made to publish results in peer-reviewed journals. Data from this study may be requested from other researchers 2 years after the completion of the primary endpoint by contacting the principle investigators. Considerations for ensuring confidentiality of these shared data are described in Section 10.1.3.

In addition, this study will comply with the NIH Genomic Data Sharing Policy, which applies to all NIH-funded research that generates large-scale human or non-human genomic data, as well as the use of these data for subsequent research. Large-scale data include genome-wide association studies (GWAS), single nucleotide polymorphisms (SNP) arrays, and genome sequence, transcriptomic, epigenomic, and gene expression data.

10.1.12 CONFLICT OF INTEREST POLICY

The independence of this study from any actual or perceived influence, such as by the pharmaceutical industry, is critical. Therefore, any actual conflict of interest of persons who have a role in the design, conduct, analysis, publication, or any aspect of this trial will be disclosed and managed. Furthermore, persons who have a perceived conflict of interest will be required to have such conflicts managed in a way that is appropriate to their participation in the design and conduct of this trial according to the guidelines set forth by the Conflict of Interest Program at UNC.

10.2 ADDITIONAL CONSIDERATIONS

N/A.

10.3 ABBREVIATIONS AND SPECIAL TERMS

The list below includes abbreviations utilized in this template. However, this list should be customized for each protocol (i.e., abbreviations not used should be removed and new abbreviations used should be added to this list). Special terms are those terms used in a specific way in the protocol. For instance, if the protocol has therapist-participants and patient-participants, those terms could be included here for purposes of consistency and specificity.

AE	Adverse Event
ANCOVA	Analysis of Covariance
CFR	Code of Federal Regulations
CLIA	Clinical Laboratory Improvement Amendments
CMP	Clinical Monitoring Plan
COC	Certificate of Confidentiality

CONSORT	Consolidated Standards of Reporting Trials
CRF	Case Report Form
DCC	Data Coordinating Center
DHHS	Department of Health and Human Services
DSMB	Data Safety Monitoring Board
DRE	Disease-Related Event
EC	Ethics Committee
eCRF	Electronic Case Report Forms
FDA	Food and Drug Administration
FDAAA	Food and Drug Administration Amendments Act of 2007
FFR	Federal Financial Report
GCP	Good Clinical Practice
GLP	Good Laboratory Practices
GMP	Good Manufacturing Practices
GWAS	Genome-Wide Association Studies
HIPAA	Health Insurance Portability and Accountability Act
IB	Investigator's Brochure
ICH	International Council on Harmonisation
ICMJE	International Committee of Medical Journal Editors
IDE	Investigational Device Exemption
IND	Investigational New Drug Application
IRB	Institutional Review Board
ISM	Independent Safety Monitor
ITT	Intention-To-Treat
LSMEANS	Least-squares Means
MedDRA	Medical Dictionary for Regulatory Activities
MOP	Manual of Procedures
NCT	National Clinical Trial
NIH	National Institutes of Health
NIH IC	NIH Institute or Center
OHRP	Office for Human Research Protections
PI	Principal Investigator
QA	Quality Assurance
QC	Quality Control
SAE	Serious Adverse Event
SAP	Statistical Analysis Plan
SMC	Safety Monitoring Committee
SOA	Schedule of Activities
SOC	System Organ Class
SOP	Standard Operating Procedure
UP	Unanticipated Problem
US	United States

10.4 PROTOCOL AMENDMENT HISTORY

The table below is intended to capture changes of IRB-approved versions of the protocol, including a description of the change and rationale. A **Summary of Changes** table for the current amendment is located in the **Protocol Title Page**.

Version	Date	Description of Change	Brief Rationale
1.0	2/12/20	Initial Protocol Document	This serves as the current protocol approximately 6 weeks before first participant is enrolled. We anticipate an updated Version 1.1 to be submitted before enrollment of the first participant.
1.1	2/26/20	Step 5, Section 5.5 updated	Step 5 updated to allow enrollment goal of 40% for sub-groups with fewer potential participants available for enrollment
1.2	2/28/20	Stool protocol added	To asses change in stool microbiome in response to the interventions. This protocol was submitted to the UNC IRB on 3/2/20 and approved on 3/12/10.
1.3	2/22/21	Update protocol for Wave 2 recruitment	Wave 2 practices are smaller so will use cycle size of 60.
1.4	3/4/21	Protocol for physician review of EHR added	Protocol update.
1.5.	3/25/21	Sec 8.1.3a. Protocol amended to include time intervals for study activities after hospitalization: Sec 8.1.3a	Self-explanatory
1.6	3/25/21	Sec. 8.1.3.3 a. Phlebotomy protocol update intervals for collection study samples after randomization visit and collection of specimens at UNC labs.	Self-explanatory
1.7	7/25/21	Sec. 8.2. Decision made to send Epic staff message to PCP for LDL > 190 and not otherwise addressed in the medical record.	Self-explanatory
1.8	11/4/21	Sec 5.2. HIV controlled defined as undetectable RNA and CD4 count above 400.	Self-explanatory
1.9	6/8/25	Entire protocol reviewed with minor edits to confer changes to protocol.	Self-explanatory

## List of Abbreviations

|        |  |
|--------|--|
| DELISH | Delicious Eating for Life in Southern Homes            |
| Med    | Mediterranean  |
| HPDP   | UNC Center for Health Promotion and Disease Prevention |
| WW     | Weight Watchers  |

2

## Date of current draft.

The draft was prepared on 9/10/24, after all participants were randomized but before analysis of outcomes.

3

## Introduction

The DELISH (Delicious Eating for Life in Southern Homes) Study will test if a weight loss intervention emphasizing a healthful eating pattern (Med-style) can yield long-term weight loss and improved CVD risk profiles.

Patients were recruited from 7 primary care practices located in the Chapel Hill area of central NC. Study participants were randomized to the Med-Style Weight Loss Intervention (hereafter called Med-South Intervention) or Augmented Usual Care (Weight Watchers™ and also called WW™ during the time frame of this study) in 1:1 ratio. The interventions are given free of charge. Study measurement visits are at baseline and 4-, 12-, and 24-month follow-up.

4

## Objectives

a) The primary objective of the DELISH Study is to determine if mean weight loss in the intervention group will exceed that in augmented usual care by  $\geq 4\%$  of initial body weight (e.g.,  $\geq 5\%$  intervention,  $\sim 1\%$  control).

Secondary objectives include:

b) assessing difference between study groups in proportion losing  $\geq 5\%$  body weight and differences in mean weight loss and proportion losing  $\geq 5\%$  across 3 pre-specified subgroups: 1) with vs. without diabetes; 2) females vs. males; and 3) Whites vs. African Americans,

c) assessing change in blood pressure, A1c, markers of inflammation, skin carotenoids, and self-reported dietary patterns by study group,

d) assessing process variables (attendance, fidelity, and acceptability of the Med-style dietary intervention), and key behavioral and psychosocial variables, including self-regulation/monitoring skills, self-efficacy, motivation, and quality of life, and

e) assessing implementation cost, and incremental cost-effectiveness of the intervention relative to control in terms of cost per percentage reduction in weight (i.e., kg lost) and cost per quality adjusted life years (QALYs) gained.

5

## Study Design

5.1

### Randomization and Blinding

This is a single-site (per NIH definition) open-label randomized controlled trial enrolling 360 participants for 7 local practices desiring weight loss and followed over 24 months. Participants were enrolled in 3 sequential waves as described below. Participants were randomized in 1:1 ratio. Statistician will be blinded for the primary analyses.

Group 1: Med-South Weight Loss Program (the intervention)

Group 2: Weight Watchers (WW™) (augmented usual care)

Randomized assignment were done by a computer program stratifying on Wave and diabetes status and using randomly permuted blocks of random sizes (4 and 6) to achieve balance in the participants' allocation.

## **5.2                   Planned Enrollment**

The overall sample size is 360. The study plan was to conduct contemporaneous enrollment of sub-groups to ensure that at least 40% of participants will be African American, diagnosed with diabetes, and male. At the initial study practice, the UNC General Internal Medicine practice, the contemporaneous enrollment protocol was followed for the enrollment of approximately ½ the sample, after which there were not sufficient potential participants in sub-groups of interest to continue this protocol. Instead, complete sampling was done of specific of subgroups of interest (e.g. African American men).

Enrollment was conducted in 3 sequential waves. Wave 1 included the large UNC General Internal Medicine practice located in Chapel Hill, NC. Wave 2 included two internal medicine practices in Chapel Hill, NC (Chapel Hill Internal Medicine and UNC Internal Medicine at Weaver Crossing) and one family medicine practice in Hillsborough, NC (Orange Family Medicine Group). Wave 3 included two family medicine practices in Durham, NC (UNC Family Medicine Center at Durham and UNC Family Medicine at Southpoint) and one internal medicine and pediatrics practice located near Chapel Hill, NC (North Chatham Pediatrics & Internal Medicine). Study enrollment and measurement visits were conducted at the Center for Health Promotion and Disease Prevention, located at [name]. For the Med-South intervention group, the first counseling session was conducted in person with the large majority of follow-up visits conducted by phone. For the WW group, the intervention was primarily given via web-based app for use on personal computers, tablets, or smart phones. WW participants had the option to attend group sessions once these were offered by WW after closure due to the Covid 19 pandemic.

## **5.3                   Study Medication**

None.

## **5.4                   Assessments**

Our enrollment dataset will include participants' screening ID, diabetes status, sex, and race. All these variables were obtained from the UNC electronic health record. In addition, we will ask participants to report race on our demographic form and this will be the official race variable).

Participants will be assessed according to the schedule described below.

Study data will be collected at measurement visited conducted at baseline, 4, 12, and 24 months. Process data for the intervention group (Med-South Weight Loss Program) will be collected as part of the intervention via the web-based platform and via REDCap questionnaires completed by counselors immediately after counseling sessions. Process data for the WW group will be assessed via a Data Use Agreement with WW™ and by REDCap questionnaire completed by study participants just prior to or at the follow-up measurement visits. As recommended by NIH, our measures include ADOPT core constructs (in blue) and specific instruments (in blue underlined) as noted in Table 1 below, with more detail provided in Appendix A.

Original study windows for follow-up measures as outlined below:

- 4 months: 3-8 months.
- 12 months: 11-18 months.
- 24 months: 23-30 months.

After data review, but before analysis of outcomes, these allowable windows were revised because for a variety of reasons (covid-10 issues, behind in counseling visit sequence, etc.) participants returned later than expected. Following up windows were expanded at 4 and 12 months to include the number of months after anticipated visit above to number of months after observed median follow-up date. 24 month interval was not changed as all participants were instructed to return within 30 months of randomization.

- 4 months: 3-8 months, change to median follow-up days (154), plus 4 months (4 x 30.4 [days in month] to yield 276 for end of interval. Operational interval is 90-276 days
- 12 months: 11-18 months, change to median follow-up dates (414), plus 6 months (6 x 30.4 [days in month] to yield 596 for end of interval. Operational interval is 335-596 days
- 24 months: 23-30 months, change to median follow-up dates (772), plus 6 months (6 x 30.4 [days in month] to yield 954 for end of interval. Operational interval is 700-954 days

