1.3 SCHEDULE OF ACTIVITIES

The schedule of study activities is outlined in the flow diagram below. Please note, this diagram was prepared January, 2020 and is correct for Phase I study activities. As of January, 2020, Phases II and III are still being refined. These phases will be undated in Version 2 (for Phase II) and Version 3 (Phase III) of this protocol document. Also, please note the following study activities prior to Baseline Measures.

[figure not shown]
Recruitment and Enrollment will occur during two phone calls.

- Eligibility phone call. Patients who are referred to the study by their primary care provider will be called to assess interest and eligibility. Anticipated call duration is 10-15 minutes. If interested and eligible, the potential participant will be sent the study consent form and asked to review before the consent phone call.
- Consent phone call. This call is planned for 1-2 weeks after the eligibility call and is expected to last 20 to 30 minutes. Study staff will review the study in detail going over each key component of the consent form. If the potential participant agrees to participate, he/she will be invited to document consent through an IRB approved e-consent process. If the participant does not wish to use e-consent, he/she will give verbal consent and will sign the consent form at the enrollment visit, depicted on the diagram as “baseline measures.” Note, the IRB has granted the study a waiver to collect baseline questionnaire data based on verbal consent. After the consent phone call, those who agree to participate will be encouraged to complete baseline questionnaires on-line (using REDCap) or by phone before the enrollment visit.

Allowable window for measurement and counseling visits.

- Allowable windows for measurement visits.
 - 4 month: 3-8 months.
 - 12 months: 11-18.
 - 24 months: 23-30.
- Allowable visits for counseling visits.
 - See flow diagram for sequence. The sequence will be followed as in the flow diagram. If a participant is falling behind the timeline, counseling visits may need to be truncated to allow the appropriate next measurement visit to occur within the allowable window.

Flow Diagram Outlining Intervention

*Counseling sessions: intervention format is web-based. Face-to-face counseling will be done using web-based interface. For phone counseling, participants have the option of accessing the web-based program or using a paper version.

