## **6.2 Intent-to-Treat Population (ITT) using Missing Weights from the Medical Record**

For missing weights, we will review the electronic health record and use weights as follows:

Weights will be used if they fall within the time frame allowed for follow-up measurement visits (see above Sect 5.4) and if consistent with prior weights (to avoid the occasional situation where pounds are mistakenly entered as kilograms). If more than one weight is available within the specified time window, the weight closest to the median for the window will be used. After the additional of weights so identified from the electronic medical record, we anticipate less than 5 % of follow-up weights will be missing.

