## **6.6 Sensitivity Analysis and missing data**

As outlined above, we will obtain weights from the electronic health record for study participants who did not return for measurement visits. These weights are collected on high quality electronic scales. The weight protocol in the clinic does not include removing shoes, though we expect some variability of shoe removal. We will not adjust weights obtained from the medical record for shoe removal.

After adding weights within range from the electronic health record, we anticipate that > 90% of study participants will have weights within the specified measurement windows. After including these weights, we anticipate missing weights will be less than 5%. If less than 5% of weights are missing at 24 months, the data will be analyzed by linear mixed models. If 5% or more of the weights at 24 months are missing, we will proceed as follows.

We made every effort to prevent missing data and to minimize attrition, however some dropouts occurred. We know the reasons for some dropouts but not all cases. We also know that some dropouts may be related to the underlying weight outcome so the missingness is not random. To address the missing data, we will first compare respondents and non-respondents for differences on values of selected baseline variables to assess for missing at random. We will also conduct a series of sensitivity analyses to evaluate the robustness of conclusions drawn from the primary model to departures from missing at random (MAR) assumption by comparing the magnitude of the primary treatment contrast. The linear mixed model with maximum likelihood estimation is capable of dealing with data that are MAR. In case data are not missing at random, we will use 1) multiple imputation to include auxiliary information about the missingness; 2) shared-parameter models where one variable is the efficacy outcome and the second variable is time to dropout, linked by a set of latent variables that are assumed to influence both the outcome and the time to dropout; (3) patterning-mixture model, with models for each pattern of missingness (e.g., by study phase); and (4) worst-case imputation, with baseline carried forward for intervention participants and best observation carried forward for control participants.

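### SAP 5.4 says the 24-month window was left unchanged, yet sets its upper limit at day 954, about 42 days past 30 months

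*SAP*

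**What the plan says.** Protocol 1.3 gives the allowable window in months: "24 months: 23-30". SAP 5.4 repeats this as the starting position and then reports a revision: "After data review, but before analysis of outcomes, these allowable windows were revised". It names the visits affected, "Following up windows were expanded at 4 and 12 months", and sets the last visit apart: "24 month interval was not changed as all participants were instructed to return within 30 months of randomization".

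The list that follows treats all three visits alike. The 24-month entry reads "24 months: 23-30 months, change to median follow-up dates (772), plus 6 months" and closes with "Operational interval is 700-954 days".

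Two later sections depend on this window. SAP 6.2, on health-record weights used where a study weight is missing, states: "Weights will be used if they fall within the time frame allowed for follow-up measurement visits". SAP 6.6 counts missing weights after those records have been added, and makes the further missing-data analyses conditional: "If 5% or more of the weights at 24 months are missing, we will proceed as follows".

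**The concern.** The sentence and the bullet cannot both be right. The reason given for leaving the 24-month window alone is the 30-month limit, and the bullet goes past it.

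The primary contrast is at 24 months, so this is the window that matters most. A weight dated between the two limits is either a valid 24-month weight or a missing one, depending on which statement is followed. In the SAP 6.2 analysis that decides whether a health-record value enters. In SAP 6.6 it changes the count compared with 5%. Moving the upper limit later admits more weights and excludes none, so the missing count can fall or stay the same, and the SAP's conditional sensitivity analyses can only become less likely to be required.

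**Working it through.** **Inputs, all from SAP 5.4 unless stated:** 30.4 days per month; starting windows of 3-8, 11-18 and 23-30 months; observed medians of 154, 414 and 772 days; additions of 4, 6 and 6 months; operational ends at days 276, 596 and 954. Sample size 360 (SAP 5.2).

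**1. Reproduce the printed ends** (median + added months × 30.4).
- 4 months: 154 + 4 × 30.4 = 275.6, printed 276.
- 12 months: 414 + 6 × 30.4 = 596.4, printed 596.
- 24 months: 772 + 6 × 30.4 = 954.4, printed 954.

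All three reproduce, so day 954 is not a slip in calculation.

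**2. Convert the starting upper limits to days and compare.**
- 4 months: 8 × 30.4 = 243.2; moved by 276 − 243.2 = 32.8 days.
- 12 months: 18 × 30.4 = 547.2; moved by 596 − 547.2 = 48.8 days.
- 24 months: 30 × 30.4 = 912; moved by 954 − 912 = 42 days, to 954 / 30.4 = 31.4 months.

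The window described as unchanged moved more than one of the two described as expanded. Its lower limit did not move in effect: 23 × 30.4 = 699.2, printed 700. The span grows from 912 − 700 = 212 days to 954 − 700 = 254 days, or 42 / 212 = 19.8%.

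**3. Vary the month length.** The SAP is not wholly consistent: 3 × 30.4 = 91.2, but its 4-month window opens at day 90, which is 3 × 30.
- 30.0 days: 30 months = 900, gap 54.
- 30.4375 days: 913.1, gap 41.
- 31 days: 930, gap 24.
- Reading 30 months as running to the end of the 30th month, at 30.4 days: 31 × 30.4 = 942.4, gap 11.6, about 12.

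Only stacking the two most generous readings (31 months of 31 days, day 961) reaches past 954, and that abandons the SAP's stated month length.

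**4. The trigger.** 0.05 × 360 = 18 missing weights at 24 months.

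**5. How a late health-record weight could enter.** Where several records qualify, SAP 6.2 takes the one nearest the window's median. If that is the observed 772:
- days 700-912 lie at most 912 − 772 = 140 days away;
- days 913-954 lie 141 to 182 days away.

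A late record is then used only when the participant has no earlier one in the window. If the midpoint is meant, (700 + 954) / 2 = 827, this ordering fails: day 913 is 86 days away and day 700 is 127.

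**The case against.** The strongest reply is that nothing is hidden. Day 954 is printed beside the faulty sentence, the paragraph opens by saying the windows were revised, and the SAP places the revision before any outcome analysis. On this view it is a wording conflict. The disclosure point stands: a careful reader of SAP 5.4 sees both statements. It does not tell that reader which one governed the data.

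A second reply is that the bullet may be a mechanical repeat of the 4- and 12-month text, with the sentence correct. That also stands as a possibility. The documents do not show which limit was applied, so neither day 912 nor day 954 can be declared right from the text.

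Third, the reach is limited. Health-record weights belong to the SAP 6.2 analysis, not to the ITT population of 6.1, and on the day-772 reading late records enter only for participants with no earlier qualifying record. SAP 9.4.1 takes all observed follow-up data and does not say whether the window restricts study-visit weights. This narrows the point. It leaves the SAP 6.6 trigger exposed, because participants who have only a late weight are the ones whose missing status changes.

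A reader might infer that the window was stretched to keep missingness under 5%, or that the primary result is biased. The documents support neither: they give no count of weights on days 913-954, no split by arm, and no sign that outcomes informed the revision.

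**Conclusion.** The contradiction is real and sits within the current text of SAP 5.4. The printed upper limit is 42 days past 30 months at the SAP's own conversion, and about 12 to 54 days past it when the month length or the meaning of 30 months is varied on its own. The figure of 42 rests on the 30.4-day month; the direction holds under each of those readings.

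The consequence is confined to which health-record weights qualify under SAP 6.2, the missing count compared with 18 of 360 under SAP 6.6 and, if study-visit weights are also windowed, which late visits count. The effect on the treatment contrast and on the trigger cannot be sized from the documents. Severity lies between minor and should-fix: reconciliation is cheap and the window belongs to the primary time point, but no harm to the result is shown.

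**What to change.** - Add a dated SAP note stating which upper limit was actually applied to the 24-month data and when it was set. Correct the sentence or the bullet, whichever is wrong. Do not change the applied limit now: SAP 9.4.1 records a review of the analysis in May 2025, so a switch in either direction would be post hoc.
- State in SAP 9.4.1 whether the window restricts study-visit weights in the mixed model.
- Report by arm the number of weights dated after day 912 and the 24-month missing count at day 912 and at day 954. Run the limit that was not applied as a labelled sensitivity analysis.
- Run the missing-data sensitivity analyses whichever limit holds. Protocol 9.4.2 promises the same four (multiple imputation, shared-parameter, pattern-mixture and worst-case imputation) with no threshold, so they should not hang on a count that the window can alter.

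The cost is one note, one sentence in 9.4.1, a small table of counts and one extra model run. The four missing-data analyses are work that the protocol already commits to.
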